**List of Abbreviations**

Abbreviation	Definition
AE	adverse event
AESI	adverse event of special interest
ANCOVA	analysis of covariance
AR	adverse reaction
bAb	binding antibody
BMI	body mass index
CI	confidence interval
CDC	US Centers for Disease Control and Prevention
COVID-19	coronavirus disease 2019
CRO	contract research organization
CSP	clinical study protocol
CSR	clinical study report
DHHS	Department of Health and Human Services
DSMB	Data Safety Monitoring Board
eCRF	electronic case report form
eDiary	electronic diary
EoS	end of study
FAS	Full Analysis Set
FSH	follicle-stimulating hormone
GLSM	geometric least square mean
GM	geometric mean
GMFR	geometric mean fold rise
GMR	geometric mean ratio
GMT	geometric mean titer
HAI	hemagglutination inhibition
IM	intramuscular
IP	investigational product
IRT	interactive response technology
LLOQ	lower limit of quantification
MAAE	medically attended adverse event
MedDRA	Medical Dictionary for Regulatory Activities
mRNA	messenger ribonucleic acid
nAb	neutralizing antibody

Abbreviation	Definition
NP	nasopharyngeal
PP	Per-Protocol
PT	preferred term
RT-PCR	reverse transcriptase polymerase chain reaction
SAE	serious adverse event
SAP	statistical analysis plan
SARS-CoV-2	severe acute respiratory syndrome coronavirus 2
SAS	Statistical Analysis System
SD	standard deviation
SOC	system organ class
SoE	schedule of events
TEAE	treatment-emergent adverse event
ULOQ	upper limit of quantification
WHO	World Health Organization
WHODD	World Health Organization drug dictionary

## 1. Introduction

This statistical analysis plan (SAP), which describes the planned analyses for Study mRNA-1073-P101, is based on the most recent approved clinical study protocol (CSP), Amendment 2, dated 16-Aug-2022, and the most recent approved electronic case report form (eCRF), dated 03-August-2022.

In addition to the information presented in the statistical analysis plan section of the protocol (Section 9), which provides the principal features of analyses for this study, this SAP provides statistical analysis details/data derivations. It also documents modifications or additions to the analysis plan that are not “principal” in nature and result from information that was not available at the time of protocol finalization.

Study mRNA-1073-P101 is a Phase 1/2, randomized, stratified, observer-blind study to evaluate the safety, reactogenicity, and immunogenicity of mRNA-1073 (SARS-CoV-2 and influenza vaccine) compared to co-administered mRNA-1010 (influenza) and mRNA-1273 (SARS-CoV-2) vaccines and to mRNA-1010 vaccine and mRNA-1273 vaccine alone in healthy adults 18-75 years of age.

PPD Biostatistics and Programming team, designee of Moderna Biostatistics and Programming department, will perform the statistical analysis of the safety, reactogenicity, and immunogenicity data; Statistical Analysis System (SAS) Version 9.4 or higher will be used to generate all statistical outputs (tables, figures, listings, and datasets). The SAP will be finalized and approved prior to the primary analysis clinical database lock and treatment unblinding for the study. If the methods in this SAP differ from the methods described in the protocol, the SAP will prevail.

In this document, study vaccination, injection of investigational product (IP)/investigational vaccine, and injection are used interchangeably.

## 2. Study Objectives

### 2.1. Primary Objectives

The primary objective is to evaluate the safety and reactogenicity of study vaccines.

### 2.2. Secondary Objectives

The secondary objectives are:

- To evaluate the humoral immunogenicity to vaccine-matched strains for influenza and SARS-CoV-2 across study vaccine arms at Day 29
- To evaluate the humoral immunogenicity to vaccine-matched strains for influenza and SARS-CoV-2 at all evaluable humoral immunogenicity time points

### 2.3. Exploratory Objectives

The following exploratory objectives may be performed:

- To evaluate the humoral immunogenicity against vaccine mismatched strains
- To evaluate the humoral immunogenicity against vaccine-matched and mismatched strains using alternative methods (eg, microneutralization assay for influenza or ligand-binding assay for SARS-CoV-2)
- To evaluate cellular immunogenicity in a subset of participants
- To further characterize the immune response across study vaccines
- To assess the occurrence of clinical influenza and COVID-19 in study participants and characterize their immune response to infection and viral isolates

## 3. Study Endpoints

### 3.1. Primary Endpoints

The primary objective will be evaluated by the following endpoints:

- Frequency and grade of each solicited local and systemic reactogenicity AR during a 7-day follow-up period post vaccination
- Frequency and severity of any unsolicited adverse events (AEs) during the 28-day follow-up period post vaccination
- Frequency of any serious adverse events (SAEs), adverse events of special interest (AESIs), medically attended adverse events (MAAEs), and AEs leading to discontinuation from Day 1 to Day 181/EoS

### 3.2. Secondary Endpoints

The secondary objective will be evaluated by the following endpoints:

- Geometric mean titer (GMT) and geometric mean fold rise (GMFR) at Day 29 compared with Day 1 (baseline) by hemagglutination inhibition (HAI) assay for influenza and PsVNA (or binding antibody assay) for SARS-CoV-2
- Influenza: Percentage of participants with seroconversion, defined as a Day 29 titer  $\geq 1:40$  if baseline is  $< 1:10$  or a 4-fold or greater rise if baseline is  $\geq 1:10$  in anti-HA antibodies measured by HAI assay
- SARS-CoV-2: Percentage of participants with seroresponse, defined as a Day 29 titer  $\geq 4$ -fold if baseline is  $\geq$  LLOQ or  $\geq 4 \times$  LLOQ if baseline titer is  $<$  LLOQ in neutralizing antibody (nAb) titers measured by PsVNA (or binding antibody assay).
- GMT and GMFR compared with Day 1 (baseline) by HAI for influenza and PsVNA (or binding antibody assay) for SARS-CoV-2
- Percentages of participants with seroconversion (influenza) and seroresponse (SARS-CoV-2) as defined above

### 3.3. Exploratory Endpoints

The exploratory objectives may be evaluated by the following endpoints:

- GMT and GMFR (compared to Day 1) to vaccine mismatched strains
- GMT and GMFR (compared to Day 1) to vaccine-matched and mismatched strains assayed by alternative methods (eg, microneutralization assay for influenza or ligand-binding assay for SARS-CoV-2)
- Frequency, magnitude, and phenotype of virus-specific T-cell and B-cell responses measured by flow cytometry or other methods, and to perform targeted repertoire analysis of B cells and T cells after vaccination
- Frequency, specificities, or other endpoints to be determined for the further characterization of immune responses
- Frequency of laboratory-confirmed clinical influenza and COVID-19 and assessment of immune responses to infection and viral isolates

## 4. Study Design

### 4.1. Overall Study Design

[figure not shown]
This is a Phase 1/2, randomized, stratified, observer-blind study to evaluate the safety, reactogenicity, and immunogenicity of mRNA-1073 compared to co-administered mRNA-1010 and mRNA-1273 vaccines and to the individual vaccines alone in healthy adults 18 to 75 years of age.

The study will enroll approximately 550 generally healthy adults 18 to 75 years of age who were previously fully vaccinated for COVID-19 primary series with a locally authorized and approved SARS-CoV-2 vaccine, and their last COVID-19 vaccine (primary series or booster) must be  $\geq$  120 days prior (or less per local guidance) to the randomization visit. Participants must not have received a licensed influenza vaccine within  $\leq$  180 days of randomization and have no known history of confirmed influenza infection within  $\leq$  180 days or SARS-CoV-2 infection within  $\leq$  90 days of Screening. The numbers of participants and groups are shown in [Table 1](#).

**Table 1 Study Arms**

#	Group Name	Sample Size (N=550)
1	mRNA-1273 CCI + placebo	50
2	mRNA-1010 CCI + placebo	100
3	mRNA-1010 CCI + mRNA-1273 CCI co-administration	100
4	mRNA-1073 CCI + placebo	100
5	mRNA-1073 CCI + placebo	100
6	mRNA-1073 CCI + placebo	100

All participants of the study will participate in a Screening period (up to 28 days before Day 1), treatment period (single dose of vaccine on Day 1), and a follow-up period (up to 6 months after vaccination). The study schema is presented in [Figure 1](#). Please refer to Table 1 in the protocol for Schedule of Events (SoE).

**Figure 1** Study Schema

## 4.2. Statistical Hypotheses

No formal hypotheses will be tested. All analyses will be descriptive using observed data only, and presented by vaccine group.

## 4.3. Sample Size and Power

The sample size for this study is not driven by statistical assumptions for formal hypothesis testing. The number of proposed participants is considered sufficient to provide a descriptive summary of the safety and immunogenicity of different study groups.

The study will enroll approximately 550 generally healthy adults 18 to 75 years of age who were previously fully vaccinated for COVID-19 primary series with a locally authorized and approved SARS-CoV-2 vaccine, and their last COVID-19 vaccine must be  $\geq 120$  days prior to the randomization visit (or less per local guidance). Participants must not have received a licensed influenza vaccine within  $\leq 180$  days of randomization and have not had known

history of confirmed influenza infection within  $\leq$  180 days or SARS-CoV-2 infection within  $\leq$  90 days of Screening. The number of participants and groups are shown in Table 1.

Approximately 550 participants will be enrolled at a CCI [REDACTED]. A sample size of 100 participants in one group has at least an 85% (or 95%) probability to observe at least 1 participant with an AE at a true 2% (or 3%) AE rate(Table 2).

**Table 2 Randomized Sample Size Calculations**

Sample Size	True AE Rate	Probability to Observe 0 AEs	Power to Detect at Least 1 AE
50	0.05	7.7%	92.3%
50	0.03	21.8%	78.2%
100	0.03	4.8%	95.2%
100	0.02	13.3%	86.7%

Abbreviation: AE = adverse event.

#### 4.4. Randomization

Randomization will be performed using an interactive response technology (IRT). Participants will be randomized in a CCI [REDACTED] to receive mRNA-1273 (CCI [REDACTED]) + placebo (50 participants), mRNA-1010 (CCI [REDACTED]) + placebo (100 participants), mRNA-1010 (CCI [REDACTED]) + mRNA-1273 (CCI [REDACTED]) co-administration (100 participants), mRNA-1073 (CCI [REDACTED]) + placebo (100 participants), mRNA-1073 (CCI [REDACTED]) + placebo (100 participants), or mRNA-1073 (CCI [REDACTED]) + placebo (100 participants). Randomization will be stratified by age (18 to 49 years old and 50 to 75 years old, balanced across the 2 age groups within each vaccination group).

#### 4.5. Blinding and Unblinding

This is an observer-blind study. The investigator, study staff, study participants, site monitors, and Sponsor personnel (or its designees) will be blinded to the IP administered until the study database is locked and unblinded, with certain exceptions (please refer to Section 9.1 of the protocol for details).

An independent unblinded statistical and programming team will perform the preplanned IA ([Section 6.7.1](#)). Sponsor team members will be prespecified to be unblinded to the IA results and will not communicate the results to the blinded investigators, study site staff, clinical monitors, or participants.

The Data Safety Monitoring Board (DSMB) will review unblinded safety data provided by the independent unblinded statistician to safeguard the interests of clinical study participants and to help ensure the integrity of the study. The DSMB will also review unblinded statistical outputs for ad hoc safety reviews triggered by pause rules, should this occur.

## **5. Analysis Sets**

### **5.1. Randomization Set**

The randomization set consists of all participants who are randomly assigned.

### **5.2. Full Analysis Set (FAS)**

The FAS consists of all randomly assigned participants who receive the IP. Participants will be analyzed according to the group to which they were randomized.

### **5.3. Per Protocol (PP) Set**

The PP set consists of all participants in the FAS who comply with the injection schedule, comply with the timings of immunogenicity blood sampling to have a baseline and at least 1 post-injection assessment and a Day 29 assessment, do not have influenza or SARS-CoV-2 infection at baseline and post-baseline up to Day 29 (as documented by positive RT-PCR testing result), and have no major protocol deviations and/or prohibited concomitant medication use (in the Protocol section 6.5.3) that are prespecified with impacts on the immune response and should be excluded from the PP analysis set. The PP set will be used as the primary analysis set for analyses of immunogenicity unless otherwise specified. Participants will be analyzed according to the group to which they were randomized.

Subjects with dosing error will be considered as having a protocol deviation. However, the determination of whether to include/exclude subjects from the PP Set due to dosing error will be based on the dosage difference (in  $\mu\text{g}$ ) between the actual dose received and the randomized dose. The PP Set exclusion criteria for subjects with dosing error are described below in Table 3.

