## 6. Statistical Analysis

### 6.1. General Considerations

All analyses will be conducted using SAS Version 9.4 or higher. Statistical outputs (tables, figures, listings, and datasets) will refer study participants as subjects and will use injection of IP and injection interchangeably.

**Continuous variables** will be summarized using the following descriptive summary statistics: the number of subjects (n), mean, standard deviation (SD), median, minimum (min), and maximum (max).

**Categorical variables** will be summarized using counts and percentages.

**Baseline value**, unless specified otherwise, is defined as the most recent non-missing measurement (scheduled or unscheduled) collected before the dose of IP in this study. For immunogenicity tests and nasopharyngeal (NP) swab tests, the baseline is defined as the most recent non-missing result/measurement (scheduled or unscheduled) collected before or on the date (and time, if available) of injection (Day 1).

For the summary statistics of all numerical variables unless otherwise specified, the display precision will follow programming standards. Please see [Appendix A](#) for variable display standards.

When count data are presented, the percentage will be suppressed when the count is zero in order to draw attention to the non-zero counts. A row denoted “Missing” will be included in count tabulations where specified on the shells to account for dropouts and missing values. The denominator for all percentages will be the number of subjects in the treatment group within the analysis set of interest, unless otherwise specified.

Symptomatic COVID-19 is defined by the presence of one of the CDC-listed symptoms (CDC [2021c](#)) and a positive RT-PCR test on a respiratory sample.

Asymptomatic SARS-CoV-2 infection is defined as a positive RT-PCR test on a respiratory sample in the absence of symptoms or a positive serologic test for anti-nucleocapsid antibody after a negative test result at the time of enrollment, with the serologic assay detecting previously resolved SARS-CoV-2 infections that may have occurred between visits, and the RT-PCR to detect active viral infection at the time of a visit.

The following analysis periods of safety analyses will be used:

- Overall period: from the day of vaccination (Day 1) and continues through the earliest date of (study completion, discontinuation from the study, or death).

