### 6.3. Efficacy analysis

While the study is not powered for efficacy assessments, symptoms of infection with respiratory pathogens will be tracked as an exploratory objective in this study. All participants will provide nasopharyngeal (NP) swab samples before the injection on Day 1 for assessment of infection with respiratory pathogens, including influenza viruses and SARS-CoV-2. Additionally, participants will be instructed to report via Symptom Reporting eDiary or telephone calls whether ILI/COVID-19 symptoms have been experienced (see [Section 8.4.5](#) and [Section 8.4.6 in Protocol](#) for symptoms), 2 times weekly from Day 1 through Day 29 and once weekly from Day 30 through Day 181/EoS.

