### 6.3.2. SARS-CoV-2 Infection

- Symptomatic COVID-19 is defined by the presence of one of the below CDC-listed symptoms (CDC [2021c](#)) and a positive RT-PCR test on a respiratory sample. Fever (temperature  $\geq 38.0^{\circ}\text{C}$  [ $100.4^{\circ}\text{F}$ ]) or chills (of any duration)
- Cough (of any duration)
- Shortness of breath and/or difficulty breathing (of any duration)
- Nausea, vomiting or diarrhea (of any duration)
- Fatigue (lasting  $\geq 48$  hours)
- Muscle or body aches (lasting  $\geq 48$  hours)
- Headache (lasting  $\geq 48$  hours)
- New loss of taste and/or smell (lasting  $\geq 48$  hours)
- Sore throat, congestion, or runny nose (lasting  $\geq 48$  hours)

Asymptomatic SARS-CoV-2- infection is defined as a positive RT-PCR test on a respiratory sample in the absence of symptoms or a positive serologic test for anti-nucleocapsid antibody after a negative test result at the time of enrollment, with the serologic assay detecting previously resolved SARS-CoV-2 infections that may have occurred between visits, and the RT-PCR to detect active viral infection at the time of a visit. The following summaries will be provided for SARS-CoV-2- infection:

- RT-PCR test results at baseline will be summarized by test and vaccination group. Participants with positive SARS-CoV-2- results at baseline will be presented in a listing.

- The number and percentage of participants with at least one positive SARS-CoV-2- result at post-baseline will be provided by vaccination group. Participants with at least one positive SARS-CoV-2- result at post-baseline will be presented in a listing.
- Participants with RT-PCR confirmed SARS-CoV-2 infection will be presented in a listing.

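### The PP set removes SARS-CoV-2 infections up to Day 29 only on a positive RT-PCR, so participants who meet the SAP's own serological definition of infection stay in the Day 29 SARS-CoV-2 analyses

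*SAP*

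**What the plan says.** SAP Section 5.3 requires that PP participants be free of influenza and SARS-CoV-2 infection from baseline through Day 29, with infection taken "as documented by positive RT-PCR testing result". The same section gives the set its role: "The PP set will be used as the primary analysis set for analyses of immunogenicity unless otherwise specified". Section 6.5 repeats that immunogenicity rests on the PP set.

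Sections 6.1 and 6.3.2 define asymptomatic SARS-CoV-2 infection in two ways. One is a positive RT-PCR without symptoms. The other is "a positive serologic test for anti-nucleocapsid antibody after a negative test result at the time of enrollment". Section 6.3.2 gives the purpose of the second route, "with the serologic assay detecting previously resolved SARS-CoV-2 infections that may have occurred between visits", and assigns RT-PCR to infection that is active when a visit takes place.

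On sampling, Section 6.3 states: "All participants will provide nasopharyngeal (NP) swab samples before the injection on Day 1". For the time after Day 1 that section describes symptom reporting, twice weekly to Day 29 and weekly thereafter. It refers to the protocol for the symptom lists.

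**The concern.** The SAP recognises that RT-PCR can miss an infection that comes and goes between visits, and it names a serological test to find such infections. For the interval that determines the Day 29 result, however, the PP rule accepts RT-PCR alone. The same participant can be infected under Section 6.3.2 and uninfected under Section 5.3.

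The sponsor has already decided that infected participants do not belong in the primary immunogenicity set, so this is not a dispute about the estimand. The rule carries out that decision only in part. The results exposed are the SARS-CoV-2 Day 29 GMT, GMFR and seroresponse rate, which are secondary endpoints, and the SARS-CoV-2 half of Table 5 in Section 6.5.2. The influenza HAI results are not affected by anti-nucleocapsid conversion.

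**Working it through.** The SAP states no figure on this point, so there is none to reproduce. The check has two parts.

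**1. Does another rule remove these participants?**

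- *Major protocol deviations (5.3, 6.2.6):* an infection after vaccination is not a departure from the protocol, so this clause does not clearly catch it.
- *Day 29 ANCOVA (6.5.2):* the terms are treatment group, log baseline titer and age stratum. None concerns infection after baseline.
- *Seroresponse differences (6.5.2):* Miettinen-Nurminen intervals, with no adjustment for infection.
- *FAS analysis (6.5):* optional, considered only if the FAS and PP set differ by more than 10%, and it would keep the same participants.

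No rule closes the gap. Those who stay are participants with anti-nucleocapsid conversion by Day 29 and no positive RT-PCR. Converters who also tested RT-PCR-positive are already excluded.

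**2. How large could the effect be?**

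Inputs from the SAP: 50 participants in Group 1 and 100 in each of Groups 2 to 6 (Table 1). Assumed, because the SAP gives neither: a share p of 1% to 5% of an arm, and an extra fold f of 2 to 5 in the Day 29 titer caused by infection.

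A share p with log titers raised by log f moves the mean log titer by p·log f. The GMT is therefore multiplied by f^p. The GMFR is multiplied by the same factor, since the baseline titer precedes the infection.

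| p | f = 2 | f = 3 | f = 5 |
|---|---|---|---|
| 1% | 0.7% | 1.1% | 1.6% |
| 3% | 2.1% | 3.4% | 4.9% |
| 5% | 3.5% | 5.6% | 8.4% |

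For example, 2^0.01 − 1 = 0.7% and 5^0.05 − 1 = 8.4%.

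*Ratio between arms A and B:* multiplied by f^(pA − pB). With pA = pB and the same f, the factor is 1. A chance imbalance can still move it. With 1 of 50 infected in Group 1 and 0 of 100 in the other group, the ratio of that group to Group 1 is multiplied by 2^(−1/50) = 0.986 at f = 2. With 3 of 50 and f = 5 it is 5^(−3/50) = 0.908. These factors ignore the covariate adjustment.

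*Seroresponse rate:* the rise is at most p × (1 − true rate). That is 0.01 × (1 − 0.90) = 0.1 percentage points at the low end and 0.05 × (1 − 0.50) = 2.5 points at the high end, with true rates of 90% and 50% assumed. In Group 1, one participant who reaches the threshold only because of infection moves the rate by 1/50 = 2 points.

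**The case against.** The strongest reply is that this is a choice and not a contradiction. Section 5.3 states its own standard of evidence in the same sentence. The broader definition mainly serves infection tracking, which Section 6.3 calls exploratory. Surveillance may use a wide definition while exclusion uses a narrow, confirmed one, and the SAP nowhere says that the two must match. This is fair as to form: the two sections can coexist. It does not explain why the interval before Day 29 should rely on the test that the SAP itself treats as incomplete between visits.

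The other limits on the point also stand:

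- **Sampling lies in the protocol.** A reader might infer from Section 6.3 that no swabs are taken after Day 1 unless symptoms are reported, so that every symptom-free infection escapes the PP rule. The SAP does not support this. The Schedule of Events is in the protocol, and Section 6.3.2 leaves room for RT-PCR at later visits.
- **The serology schedule is unknown.** Anti-nucleocapsid antibody is not among the analytes in Section 6.5.1, and the SAP gives no sampling day for it. A Day 29 criterion works only if a sample is tested by then.
- **Serology also has gaps.** Section 4.1 bars only known SARS-CoV-2 infection within 90 days of Screening, so some participants may be anti-nucleocapsid-positive at enrollment. They cannot convert.
- **Exclusion has its own cost.** Removing participants for something that happens after randomization can itself select differently by arm, and an antigen-specific exclusion would split the single PP set.
- **Little depends on it.** No hypotheses are tested (Section 4.2), Table 5 is labelled exploratory, and the primary endpoints concern safety.

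**Conclusion.** The point holds as an incomplete exclusion rule. Participants who convert by Day 29 without a positive RT-PCR are infected by the SAP's definition, stay in the primary immunogenicity set, and contribute any infection-related rise to the Day 29 SARS-CoV-2 results. Nothing else in the SAP removes or adjusts for them.

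The effect is probably small. The range of 0.7% to 8.4% for an arm GMT rests wholly on the assumed 1% to 5% share and 2- to 5-fold extra titer. Between-arm ratios are not shifted on average if infection is equally frequent and acts equally in both arms. Group 1, with 50 participants, is the arm most exposed to a chance imbalance. Because all analyses are descriptive, neither alpha nor power is affected.

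A reader might go further and infer that weaker regimens would have more infections, so that the bias hides dose differences. The SAP gives no support for that. Every group in the SARS-CoV-2 comparisons receives a SARS-CoV-2 vaccine component, and nothing indicates that infection by Day 29 depends on regimen.

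**What to change.** Keep the single PP set. For the Day 29 SARS-CoV-2 GMT, GMFR, seroresponse and Table 5 comparisons, prespecify a further analysis in Section 6.5.2 that also excludes participants whose anti-nucleocapsid result goes from negative at enrollment to positive by the Day 29 sample, where that sample is tested. The alternative is to add the criterion to Section 5.3. That is shorter to write, but it also removes converters from the influenza analyses unless the PP set is split by antigen.

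The wording should be settled before the Day 29 interim analysis (Section 6.7.1), so that the exclusion is not chosen after results are seen, and the anti-nucleocapsid schedule should be checked against the protocol first.

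The cost is a short paragraph and a repeat set of tables. A few participants are lost from that analysis. It does not cover infections too close to Day 29 to have converted, or infections in participants already anti-nucleocapsid-positive at enrollment. If the Day 29 sample is not tested, the analysis cannot be run, and the SAP should state that limitation.
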